**Table 2. Timeline of Major Goals** 

#### 2a.3.a. Study Settings

Dissemination

All work will be carried out in the PTSD outpatient clinic of the VASDHS. [name] (co-mentor) is the Director of the PTSD clinic and shows a long-standing ability to recruit patients to participate in research (see Letter of Support). The staff at the PTSD clinic includes clinical psychologists, social workers, program assistant, and trainees (psychiatry residents, psychology interns and postdoctoral fellows, and social work interns). As observed in past VA-funded projects of the mentors of this proposal, the close proximity between study personnel and the treatment program (located on the grounds of the San Diego VA) facilitates communication and adherence to project procedures and thus, increases the overall feasibility of the proposed work.

#### 2a.3.b. Recruitment Procedures

Recruitment will target Veterans with PTSD and comorbid insomnia in the outpatient PTSD clinic, MST clinic, and sleep clinic at VASDHS. In fiscal year (FY) 2013, over 21,000 Veterans sought mental health services at the VASDHS. In the FY 2013 and 2014 the PTSD clinic had 2,089 consults with 699 Veterans who showed up for three or more appointments. The MST and interpersonal trauma (IPT) clinic had 1,407 consults in FY 2013 and 2014 with 374 Veterans who showed up for three or more appointments. We have recruitment support from each clinic along with institutional support from VASDHS and the Center of Excellence for Stress and Mental Health (CESAMH; see Letter of Support). Staff in each clinic will provide a descriptive study flyer to patients newly accepted and enrolled into the outpatient PTSD program, with a diagnosis of insomnia and PTSD (based on information collected through intake). Individuals reporting interest in the study will be asked for verbal consent to be contacted by the research coordinator. In addition, informational flyers will be posted throughout the clinics with telephone number listed for interested participants to call. The research coordinator will contact prospective participants to provide an explanation of study procedures and to complete a phone-based screening. The research assessor will schedule a lab-based baseline screening visit should the individual meet basic eligibility requirements.

We will aim to recruit 2-3 participants per month for this study. [name] has recruited 4-6 participants per month with a more restricted inclusion and exclusion criteria, thus a minimum of 2-3 participants per month is feasible. Additionally, [name] is recruiting Veterans with active AUD, which we exclude for, eliminating any conflict of recruitment. The size of the proposed recruitment sample was estimated based on: (1) power analyses (see Planned Data Analysis 2a.3.j); (2) mentor experiences conducting research with similar screening procedures, designs and populations and in similar treatment settings; and (3) attrition rates reported in the literature in PTSD treatment. Based on mentors' experiences and estimates in the literature, we expect to phone screen approximately 200 Veterans to obtain 100 individuals for baseline assessment. We anticipate that 33% of Veterans will not meet inclusion/exclusion criteria following baseline assessment, resulting in 90 Veterans getting randomized to treatment. A conservatively estimated total recruitment sample of 90 will allow for up to 25% attrition, resulting in a final sample size of approximately 52 Veterans at follow-up. 52 Veterans at follow-up conservatively allow adequate power to examine all study aims.

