#### 2a.3 Research Design and Methods

**Design framework.** This proposed study will be a Stage 2 RCT comparing CBT-I integrated with PE (CBTI-PE) to a non-active sleep education component and PE (Hygiene-PE) for the treatment of male and female

Veterans with comorbid insomnia and PTSD. 90 Veterans will be enrolled through the PTSD, MST, sleep, and primary mental health treatment programs at the VASDHS. Assessments will occur at baseline, 6-weeks, post-treatment, and 3-month follow-up. All procedures will be for research purposes. Phase I start-up activities will include finalizing procedures, hiring and training research staff and therapists, and setting up of data entry and management procedures with the statistician. Phase II includes participant recruitment, enrollment, and treatment. Methods and procedures are consistent with CONSORT guidelines for conducting and reporting RCTs. We will aim to recruit 2-3 participants per month for this study. [name] has recruited 4-6 participants per month with a more restricted inclusion and exclusion criteria, thus a minimum of 2-3 participants per month is feasible. Data entry and management will begin immediately after enrollment starts with preliminary statistical analyses in the second year and continuing through the end of the study. The end of Phase II will include writing a Merit grant proposal to further examine PTSD and insomnia treatment to include other highly prevalent comorbid disorders (e.g., substance use disorders) and to explore the biological mechanisms of change (i.e., fear habituation, safety learning, and executive functioning). Phase III Dissemination includes assessments, data analyses, manuscript writing, and presentations to the scientific and clinical community. See Table 2 for timeline of major project goals during the award period.

Year		1	2				3				4				5					
Quarter	1	2	3	4	1	2	3	4	1	2	3	4	1	2	3	4	1	2	3	4
Activity	Sta	rtup	Clinical Trial		Dissemination															
Finalize procedures																				
Hire and train staff																				
Recruit/Enroll																				
Collect Data																				
Clinical Trial																				
Merit Application																				
Data Analysis																				

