Study Name: Integrated CBT-I and PE on Sleep and PTSD Outcomes (Impact Study)

Document Name: Statistical Analysis Plan

NCT ID: NCT02774642

Document Creation Date: 11-20-2015

PI: [name]

Planned Data Analysis 11-13-2015

Power analyses: Sample size was determined to ensure adequate statistical power to detect between group differences in PTSD and sleep at end of treatment and 3-month follow-up. For both outcomes the effect size was estimated as d defined as $[d = |m_1 - m_2| / \sigma]$ where m_1 and m_2 are change from intake in the outcome scores of the two conditions and σ is the common within-group standard deviation of the change score.¹⁰⁹ The effect size for the between group difference in PTSD CAPS scores from intake to end of treatment was estimated from several studies that have evaluated the effect of PE^{110, 111} on PTSD. Four studies of PE have demonstrated large within group effect sizes ranging from 1.3¹¹¹ to 4.1¹¹² with an average ES of 2.5. However, given that both conditions will receive PE, and it is already known that CBTI shows large effects on insomnia (e.g., Ulmer⁸⁰ ES = 2.15), we powered on the effect of CBTI on PTSD symptoms.

Three studies reported effect sizes of CBTI on PTSD symptoms with an average ES of 1.8.⁷⁹⁻⁸¹ We conservatively used a large effect size (0.8) requiring 34 participants per group to be detected with 90% power and a two-tailed test with alpha at .05. We increased the total sample size to be randomized to $N = 90$ in anticipation of 25% study drop-out by the 3 month assessment. Overall, we believe this sample size balances three needs: (1) sufficient power to compare the study groups; (2) the reality of recruiting a sample with dual insomnia and PTSD; and (3) project cost considerations.

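### Protocol 2a.3.b: the recruitment figures do not follow from their own rates (100 less 33% is 67, not 90; 90 less 25% is about 68, not 52), and 52 conflicts with the SAP's 68

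*Protocol*

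**What the plan says.** Protocol section 2a.3.b sets out the recruitment forecast in consecutive sentences:

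- Screening: "we expect to phone screen approximately 200 Veterans to obtain 100 individuals for baseline assessment".
- Eligibility: "We anticipate that 33% of Veterans will not meet inclusion/exclusion criteria following baseline assessment, resulting in 90 Veterans getting randomized to treatment".
- Retention: the total of 90 "will allow for up to 25% attrition, resulting in a final sample size of approximately 52 Veterans at follow-up".
- Adequacy: "52 Veterans at follow-up conservatively allow adequate power to examine all study aims".

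The same section says that the sample was based in part on the power analysis. The target of 90 also appears in section 2a.3 ("90 Veterans will be enrolled through the PTSD, MST, sleep, and primary mental health treatment programs at the VASDHS") and in section 2a.3.c.

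The SAP, under Power analyses, takes d = 0.8, "requiring 34 participants per group to be detected with 90% power and a two-tailed test with alpha at .05", and then raises the randomised total to 90 "in anticipation of 25% study drop-out by the 3 month assessment". Its Missing Data paragraph repeats the 25%. On which outcome was powered, it says "we powered on the effect of CBTI on PTSD symptoms".

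**The concern.** Each of the two steps gives a starting number, a rate and a result, and in both the result does not follow. The gaps (67 against 90, and 67.5 against 52) are too large for rounding.

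The follow-up number matters most. The protocol says 52 will do, while the SAP's calculation implies 68. A reader who takes 52 as acceptable could tolerate 42% loss without noticing that the 25% allowance behind the 90% power had been exceeded.

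The screening forecast matters for resources. If 33% is the right exclusion rate, 100 assessments will not produce 90 randomised Veterans.

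The adequacy sentence raises a separate point. It covers every aim, but the SAP calculates power only for the PTSD contrast. It argues that sleep has a larger effect, and it offers nothing for quality of life or for Aims 2 and 3.

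**Working it through.** **Inputs.** From protocol 2a.3.b: 200 screened, 100 assessed, 33% excluded, 90 randomised, 25% attrition, 52 at follow-up. From the SAP, Power analyses: d = 0.8, two-sided alpha 0.05, 90% power, 34 per group, 25% drop-out, N = 90.

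**1. The SAP's own figure.** For a two-sample t-test with n per group, power comes from the noncentral t distribution with 2n − 2 degrees of freedom and noncentrality d × √(n/2). Solving for 90% power at d = 0.8 gives n = 33.83, so 34 per group and 68 in total. Allowing for drop-out, 68 / 0.75 = 90.7. The SAP's 34 and 90 both reproduce, the latter within rounding.

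**2. The protocol's steps.**

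| Step | Stated | At the stated rate | Rate needed for the stated result |
|---|---|---|---|
| Assessed to randomised | 100 to 90 at 33% exclusion | 100 × 0.67 = 67 | 1 − 90/100 = 10% |
| Randomised to follow-up | 90 to 52 at 25% attrition | 90 × 0.75 = 67.5 | 1 − 52/90 = 42.2% |

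Other readings do not rescue the chain. Taking both losses from 90 gives 90 × 0.67 × 0.75 = 45. Taking 33% off the 200 screened gives 134. Taking 25% off 67 gives 50.25, which is near 52 but requires 67 randomised rather than 90.

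**3. Power at the competing follow-up numbers** (d = 0.8, two-sided alpha 0.05, completers only).

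| At follow-up | Arises if | Power |
|---|---|---|
| 68 (34 per group) | the SAP's requirement is met | 90.2% |
| 67 (33 + 34) | 90 randomised, 25% lost | 89.7% |
| 52 (26 per group) | 52 is the real follow-up number | 80.7% |
| 50 (25 per group) | 100 assessments are a ceiling: 67 randomised, 67 × 0.75 = 50.25 | 79.1% |

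The effect detectable with 90% power is 0.80 at 34 per group and 0.92 at 26 per group.

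**4. Workload for 90 randomised at 33% exclusion.** 90 / 0.67 = 134.3, so about 135 baseline assessments. At two screens per assessment, 134.3 × 2 = 268.7, so about 270 screens. The stated 100 is 100 / 134.3 = 74% of the number needed, about a quarter short. Section 2a.3.f gives 2 to 3 hours per baseline assessment, so 35 more assessments is 70 to 105 hours.

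**5. A possible origin (inference only).** 52 / 0.75 = 69.3, close to the 67 that 100 assessments would yield. The n for 80% power at d = 0.8 is 25.52, so 26 per group, or 52. The figures around 90 therefore fit a smaller trial, as if 90 had been updated and the rest had not. The documents do not say so, and the correction does not depend on it.

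**The case against.** The strongest reply is that this is a slip in a feasibility paragraph with no effect on inference. The target of 90 is the same throughout the protocol and SAP, the SAP gives one coherent basis for it, and no document sets a retention floor or monitoring rule at 52 or 68. That is fair as far as it goes: harm follows only if someone acts on 52 or on the 100 assessments.

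Four further points deserve weight:

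- The protocol calls 52 adequate without naming a power level. At about 81% for the powered contrast, that is not false by an 80% standard. It is still not the 90% for which the SAP plans.
- The power figures are for a completer t-test. The Aim 1 mixed model uses all available data from all randomised subjects, so they are approximate.
- The documents do not settle which figure is wrong. The forecasts are attributed to mentors' experience and to literature, so the error could lie in the 33%, the 100 or the 90. The correction has to leave that choice to the sponsor.
- Reproducing the SAP's arithmetic does not establish that d = 0.8 is the right effect when both arms receive PE. That assumption was not examined here.

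None of this restores the two stated results or removes the mismatch between 52 and 68.

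**Conclusion.** The concern holds. By the plan's own rates the randomised number should be 67 and the follow-up number 67 or 68. The 52 also contradicts the SAP, whose calculation implies 68.

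If 90 are randomised and 25% are lost, power stays at about 90% and the trial loses nothing. The fall to about 81% applies only if 52 is the real follow-up number, and the fall to about 79% only if recruitment stops at 100 assessments. Both rest on d = 0.8, equal groups and a completers-only t-test. The shortfall in forecast workload, about a quarter, rests on the 33% exclusion rate and the two-to-one screening ratio being right.

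The claim of adequate power for all aims has no calculation behind it beyond the PTSD contrast, and this would remain so if 52 became 68. The paragraph should be corrected; the sample size of 90 is not undermined.

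**What to change.** Rewrite the end of section 2a.3.b so that each number follows from the one before. If the 33% stands, suitable wording is:

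> About 270 Veterans will be screened by telephone, of whom about 135 are expected to reach baseline assessment. With 33% found ineligible, 90 will be randomised. After 25% attrition, 67 or 68 (about 34 per group) are expected at follow-up, which gives about 90% power for the between-group CAPS-5 contrast in Aim 1 at d = 0.8.

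If 200 screens and 100 assessments are the right forecast for 90 randomised, change the exclusion rate to 10% instead. If 52 is intended, state 42% attrition and about 81% power, and reconcile both with the SAP.

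In every case, delete the statement that power is adequate for all aims, or limit it to the PTSD contrast.

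The cost is one paragraph of protocol text. The target of 90, the design, the analysis and, unless 52 is intended, the SAP's power calculation stay as they are. The stated screening workload rises by about a third (200 to 270) unless the exclusion rate is corrected instead.

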#### 2a.3.c. Participants

A total sample of 90 male and female Veterans with a diagnosis of insomnia and PTSD will be recruited at VASDHS.

#### 2a.3.d. Inclusion/Exclusion Criteria.

Inclusion criteria are: a) Over the age of 19 years old; b) Diagnosis of PTSD; c) Meet diagnostic criteria for insomnia; d) Enrolled at the VASDHS and living within 50 miles of the respective facility; and e) English literacy.

Exclusion criteria are: a) Unmanaged psychosis or manic episodes in past year; b) Substance/alcohol use disorder in past 6 months; c) Diagnosed (previously or by our study screen) and untreated sleep disorder other than insomnia (Sleep disorders diagnosed, but stably treated, such as obstructive sleep apnea treated with CPAP, will be allowed); d) Participation in concurrent psychotherapies targeting PTSD; Veteran can be reassessed after their PTSD treatment concludes, Veterans who are engaged in treatment for non-PTSD symptoms (e.g., 12-step programs) will be eligible; e) Severe medical or psychiatric illness that would make it difficult to regularly attend psychotherapy sessions or participate fully in the study; and f) History of moderate to severe cognitive impairment.

#### 2a.3.e. Participant Retention

[figure not shown]
The retention component of the study is informed by recommended strategies in the literature  and the training team's wealth of experience running similar studies. Throughout the course of the study simultaneous strategies will be employed at the management, staff, and participant levels to maintain participant contact and to maximize fidelity to the training protocol.

**Tracking, General Contact, Check-ins:** Throughout the course of the study simultaneous strategies will be employed at the management, staff and participant levels to maintain participant contact and to maximize fidelity to the training protocol. First, during the initial screening assessment a Locator Form^91 will be completed for each participant that includes: (1) home address, (2) email address, (3) home/work /cell phone numbers, (4) employment or school information, and (5) contact information for two additional individuals to be used if contact with the participant is lost. Tracking information will also be collected and updated at all follow-up interview points. Based on strategies successfully employed by [name] (mentor) research team, additional methods to help reduce attrition will include specialized cards (e.g., birthday cards) which will includes a change of contact information form and a toll free number of the study center for subject-initiated contact. A reminder call will be placed the day prior to participants' scheduled in-lab assessment. Research staff will mail a reminder to participants one week prior to their follow-up appointment. Therapists will be trained to check-in each session with the Veterans to facilitate adherence to the training protocol so that participants may derive maximal benefit.

**Financial Incentives:** Participants will be compensated for their time after each completed assessment. Veterans will receive \$40 for the first in-person assessment, \$60 for the post-treatment assessment, and \$75 for the follow up assessment (Total possible = \$175).

If the Veteran meets eligibility criteria based on baseline assessment, the Veteran will then be randomized into either CBTI-PE or the control condition Hygiene-PE. Veterans will be given a sleep diary to compete for 7 days to prospectively record sleep measures (e.g., "lights out," time to fall asleep, time spent awake during the

night, total sleep time, and "lights on") and be given an actigraph (a wrist watch device) which they will wear continuously for the 7-day baseline evaluation.

**Treatment Randomization:** Following baseline assessment, participants will be randomized to the intervention (CBTI-PE) or control condition (Hygiene-PE). A computer-generated randomization sequence will be provided by our statistical expert [name] (consultant), and held by a colleague not otherwise involved with the study. Randomization will be stratified by gender to ensure a balanced number of males and females are in each treatment group.

**Bi-Weekly Assessment** (approximate time = 10 minutes): During treatment, brief self-report assessments will be given every other week when the patient arrives for therapy to track quality of life, sleep, and PTSD symptoms. Additional measures will include adherence to assignments and satisfaction with treatment.

**Post-treatment Assessment** (approximate time = 2 hours): In the week following completion of the final treatment module, Veterans will be given a sleep diary to fill out for 7 days to prospectively assess sleep at post-treatment. Patients will also wear an actigraph during the post-treatment week so as to provide objective measures of sleep to compare with the subjective sleep diary reports. At the end of the post-treatment evaluation week Veterans will return to the VASDHS to turn in the diary and actigraph and will at this time be administered the same battery of clinical assessments originally given during the baseline evaluation visit.

**3-Month Follow-Up Assessment** (approximate time = 2 hours): Veterans will return to VASDHS to do the same battery of clinical assessments they completed at baseline and post-treatment. At the conclusion of the assessment, Veterans will have completed the study. Veterans who are randomized to the control condition and who are interested in receiving the standard CBT-I treatment will be provided with CBT-I treatment at the completion of their participation in the study.

Merit Pilot Data (N = 8) Evaluation of Objective PSG Assessment of Sleep (4 Overnights total): PSG will be assessed in a small sample of Veterans pre- and post treatment of CBT-I and PE in order to gather pilot data necessary for the next step in the proposed line of research and give the PI experience with using PSG in research. PSG will help inform the mechanisms (specifically REM consolidation) through which sleep affects PE treatment. The first night of PSG will be used to adapt the Veteran to the sleep laboratory environment and to screen for sleep disorders other than insomnia and will not be used for data analysis. The second night of PSG will be used to acquire objective measures of sleep and will be used in data analysis. For the overnight sleep evaluation subjects will go to bed and be awakened at their habitual sleep and wake times. The recording montage will consist of a minimum 10 electrophysiologic signals. The basic montage includes 2 electrooculograms (EOGs) referenced to a single mastoid, 6 EEGs referenced to linked mastoids [F3, F4, C3, C4, O1 and O2], a bipolar mentalis electromyogram (EMG), and an electrocardiogram (ECG). Several measures, in addition to our core montage, will be obtained. These include: 1 channel of nasal/oral airflow and 2 channels of leg-related motor activity (right and left tibial EMGs). The airflow and tibial data are used to detect obstructive sleep apnea (OSA) and periodic limb movements (PLMs), respectively. The second PSG night will be used to characterize subjects' sleep. The montage will be the same as for the first night except OSA and PLMs will not be measured. The PSG will be used to assess standard sleep continuity parameters (e.g., sleep latency, wake after sleep onset, total sleep time, sleep efficiency, and number and length of nocturnal awakenings) and sleep architecture parameters (e.g., time spent in each sleep stage), as well as to characterize sleep microarchitecture (e.g., spectral analytic measures of EEG frequency components of sleep).

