#### **Primary Outcome Measures.**

PTSD: The Clinician-Administered PTSD Scale DSM 5 (CAPS-5) is the gold-standard, semi-structured interview that corresponds to DSM-5 criteria for PTSD. The CAPS-5 shows strong reliability and validity.

Sleep: Daily Sleep Diary. Patients will complete a daily sleep diary throughout the course of treatment (14 weeks) and for one week prior to the follow-up assessment. The sleep diary includes typical subjective measures (bed time, sleep latency, number and duration of awakenings, wake time, total time in bed, sleep quality) and two calculated variables (total sleep time and sleep efficiency). Daily sleep diaries are commonly used in studies and treatment of insomnia. The primary outcomes measure of the sleep diary will be sleep efficiency.

Quality of Life: World Health Organization Quality of Life-BREF (WHOQOL-BREF) comprises 26 items, which measure the following broad domains: physical health, psychological health, social relationships, and environment. It shows strong validity and reliability.

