Missing Data. All laboratory-based measures will be reviewed for completeness immediately following collection and prior to the participant's dismissal. Despite our intensive protocol to limit participant attrition, we do expect missing data over the course of this study (i.e., 25%) and have adjusted our recruiting sample accordingly. The primary outcomes will be tested using an intent-to-treat framework. If the extent of missing data is small and the data appear to be consistent with a missing-at-random model (MAR), then the maximum-likelihood analysis using all randomized cases and the observed data is an appropriate method for handling the missing data. In the MAR model the missingness can be a function of the observed covariates and observed outcomes. The MAR assumption is effective in treatment situations.¹¹³ The critical element when conducting MAR-based analyses is to include variables related to the missingness in the statistical model.¹¹³ Potential variables we will measure that may be related to study drop out are group assignment, social *interactions*, employment status, and income. As a check on the sensitivity of our conclusions to the assumption that the missing data are MAR we will conduct pattern-mixture modeling, which is appropriate with data that is likely MAR.⁸⁷ The distinction between ignorable (MAR) and non-ignorable missingness (missing not at random; MNAR) is generally not empirically testable and we acknowledge the possibility that data may be missing not at random. Therefore, we propose to perform MNAR sensitivity analyses using pattern mixture models. With 2 follow-up assessment points there are 4 potential missing data patterns that can emerge. Some patterns will likely have small numbers of cases precluding parameter estimation for these patterns separately. In this case we will apply the Hedeker and Gibbons⁸⁷ approach that combines missing data patterns to estimates model parameters that are conditional on the missingness using a binary variable in the model to denote missing data at one or more time points.

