Data Analysis. Preliminary analyses will consist of examining the descriptive statistics of the study sample. Outliers will be assessed and variables whose distributions depart significantly from normality will be transformed. Internal consistency of scales will be examined to determine reliability. *All analyses will be run with the full, validated PTSD scales (e.g., CAPS and PCL5) and with sleep items removed from the PTSD scales.*

Primary Aim 1 (Treatment outcomes): Investigate the efficacy of CBTI-PE on PTSD, sleep, and quality of life among Veterans with co-occurring PTSD and insomnia.

Hypothesis Aim 1: Veterans who receive CBTI-PE, compared to Hygiene-PE, will demonstrate lower PTSD symptoms, better sleep efficiency, and better quality of life at follow-up.

Independent variables: Treatment group (CBTI-PE versus Hygiene-PE) and Time (Baseline 0 weeks, Post-treatment 14 weeks, Follow-up 28 weeks).

Dependent variables (three separate models): CAPS-5 scores, Sleep Diary Sleep Efficiency, WHOQOL-BREF.

Covariates: gender, age, medications, pain, depression.

Analyses Aim 1: Analyses of this data will be conducted using three separate Random Regression Models, a generalized linear model described by Gibbons et al.⁸⁶, Hedeker et al.¹¹⁴, and Laird et al.¹¹⁵ The random effects method has several advantages over more traditional analytic approaches such as a change score, end-point, or repeated measures ANOVA. This method allows the inclusion of subjects with missing data or those who were terminated early in the study, without relying on data imputation procedures. This method provides an

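### The post-treatment visit is dated from completing the final module, with no schedule for Veterans who stop therapy or finish late, while the SAP assumes weeks 14 and 28 and intent-to-treat

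*Protocol*

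**What the plan says.** Protocol section 2a.3.f starts the post-treatment diary and actigraphy week "In the week following completion of the final treatment module". The clinical battery follows: "At the end of the post-treatment evaluation week Veterans will return to the VASDHS". No other trigger is given, and no section says when, or whether, a Veteran who stops therapy is assessed.

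The other on-treatment measures also follow therapy. Under the bi-weekly assessment, "brief self-report assessments will be given every other week when the patient arrives for therapy". For the diary, which yields the primary sleep outcome, the section on primary outcome measures says: "Patients will complete a daily sleep diary throughout the course of treatment (14 weeks) and for one week prior to the follow-up assessment".

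Of the 3-month visit, section 2a.3.f says: "Veterans will return to VASDHS to do the same battery of clinical assessments they completed at baseline and post-treatment". That sentence has no completion condition, but the date from which the 3 months run is not stated.

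The SAP's Primary Aim 1 fixes the time points: "Time (Baseline 0 weeks, Post-treatment 14 weeks, Follow-up 28 weeks". Its missing-data section says: "The primary outcomes will be tested using an intent-to-treat framework". The Aim 1 analysis uses all randomised subjects and whatever data were collected at the three time points.

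**The concern.** The two timing rules agree only for a Veteran who completes 14 weekly sessions on schedule. For one who finishes late, the visit moves with the last session while the SAP still codes it as week 14. For one who stops, the protocol's trigger is never met, so on a literal reading no post-treatment assessment falls due.

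An intent-to-treat analysis needs outcomes from Veterans who stopped as well as from those who finished. If stoppers are not assessed, a decision about therapy becomes missing outcome data by rule. If they gain less than completers, the post-treatment effect is overstated for the population randomised. Outcomes not collected at the time cannot be recovered later.

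**Working it through.** **1. The plan's own figure.** The SAP uses d = 0.8, two-sided alpha 0.05 and 90% power. The two-sample t-test gives 33.8, so 34 per group (power 0.902), as stated. Allowing for 25% drop-out, 68 / 0.75 = 90.7, against the stated 90. The sample size reproduces; the point here is when outcomes are collected.

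**2. What is due for a Veteran who stops at, say, session 5, read literally.**

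| Outcome in the Aim 1 model | Baseline | Post-treatment | 3-month |
|---|---|---|---|
| CAPS-5 | collected | not triggered | no completion condition; anchor date not stated |
| Diary sleep efficiency | collected | not triggered | the week before the visit |
| WHOQOL-BREF | collected | not triggered | as CAPS-5 |

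Table 5 has no CAPS-5 at week 6, so nothing fills the gap for that outcome. WHOQOL-BREF is scheduled at week 6, but week 6 is not a time point in the Aim 1 model.

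**3. What the analysis does with the gap.** Two post-baseline visits give 2 × 2 = 4 patterns: both seen, post-treatment only, follow-up only, neither. A stopper falls into follow-up only or neither. With neither, the likelihood model predicts the post-treatment value from Veterans in the same arm who were assessed. A pattern-mixture model can let that pattern differ, but has no post-baseline outcomes in it from which to estimate the difference. With follow-up only, it has one observation per Veteran and none at post-treatment.

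**4. Possible size.** Assumptions, none of them in the documents: completers' effect 0.8 SD (the SAP's design value, applied here to completers); a share s stops in each arm; stoppers keep a fraction f of the between-arm benefit; SD unchanged. The SAP's 25% is study drop-out by 3 months. No rate of stopping therapy is given, so 25% is a stand-in and other rates are shown.

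Effect over all randomised = 0.8 × [(1 − s) + f × s]

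| s | f = 0 | f = 0.25 | f = 0.5 | f = 1 |
|---|---|---|---|---|
| 10% | 0.72 | 0.74 | 0.76 | 0.80 |
| 25% | 0.60 | 0.65 | 0.70 | 0.80 |
| 35% | 0.52 | 0.59 | 0.66 | 0.80 |

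Example: 0.8 × (0.75 + 0 × 0.25) = 0.60. If no stopper is observed after baseline and stopping is unrelated to baseline, the missing-at-random model targets about 0.80 throughout. At 25% stopping the overstatement is therefore 0 to 0.20 SD.

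**The case against.** The strongest reply is that the trigger is shorthand for the end of a 14-week course. The SAP's fixed weeks support that reading, and no section says that stopping therapy ends assessment. The study flow diagram, which might settle it, is not shown in the text available. This stands as a possible reading, but assessment staff work from the protocol's visit rule, and that rule does not say it.

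A reader might infer that the intent-to-treat result rests on therapy completers. The documents do not support that. Aim 1's hypothesis concerns outcomes at follow-up, and the 3-month visit has no completion condition. The model keeps every randomised Veteran. The SAP plans to include variables related to missingness, to run pattern-mixture analyses for data missing not at random, and to compare attrition between arms. The retention section provides locator forms, outside contacts, reminders, and payment per completed assessment. These safeguards limit the problem; they do not create a post-treatment appointment for someone who stops.

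Three further inferences should be resisted:

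- The SAP's phrase "those who were terminated early in the study" is general text on the advantages of random-effects models. It is not a rule that Veterans who stop are terminated.
- Nothing suggests that visit timing would differ by arm: the control protocol is matched on number and length of sessions.
- The fix should not be sold on power. Assuming 45 per arm, assessing everyone gives 80% power if stoppers keep no benefit (d = 0.60), 91% if they keep half (0.70) and 96% if they keep all (0.80), against 90% for 34 completers per arm at 0.8. The gain is in what is estimated.

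**Conclusion.** The concern holds as an unreconciled timing rule with a consequence for the post-treatment outcomes. The protocol's only operational trigger is completion of the final module, Veterans who stop or finish late have no schedule, and the SAP assumes fixed weeks. Read literally, stoppers' post-treatment outcomes are missing by design and are extrapolated under missing at random, with a sensitivity analysis that has little to calibrate it.

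The exposure is greatest at the post-treatment time point, which the SAP's power statement names alongside follow-up, and in the secondary aims: Aim 2 lists post-treatment CAPS-5 as its outcome, and Aim 3 lists post-treatment sleep efficiency and pre-to-post CAPS-5 change as predictors. It is smaller at follow-up, provided that visit is held for stoppers.

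On the stated assumptions, with 25% stopping in each arm, the all-randomised effect would be 0.60 to 0.80 against 0.80 in completers. It is an illustration; the documents give neither a rate of stopping therapy nor stoppers' outcomes.

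**What to change.** Reconcile protocol section 2a.3.f with the SAP's Aim 1 time points:

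- Schedule the post-treatment and follow-up assessments in stated windows from randomisation, around weeks 14 and 28, for every randomised Veteran whatever the number of sessions attended. The first window must leave room for the 7-day diary and actigraphy.
- State that stopping therapy is not withdrawal from assessment, and record the two separately.
- Keep weeks 14 and 28 as the main time coding and add a sensitivity analysis using actual assessment dates.

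This changes assessment timing only. The cost is mostly wording, plus the staff effort of bringing back Veterans who have stopped. The protocol pays $60 per post-treatment visit; if 25% of 90 stopped (about 23 Veterans) and all attended, that is 23 × $60 = $1,380. The documents do not say whether this is already budgeted. The real downside is that some late finishers will be assessed before their last session, so their post-treatment score will reflect an incomplete course.
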